9.7.2 Determination of Sample Size

A sample size of 12,000 subjects should provide the required power for the primary endpoints as follows: (revised per Amendment 02)

- For 460 MACE events to have occurred by approximately 43 months from start of the trial, providing 95% power to exclude a noninferiority margin of 1.4, assuming an annual background rate of 1.5%, 15-month accrual period, 5% annual drop-out rate, $\alpha = 0.025$, and a 1-sided test
- For 1401 MACE+ events to have occurred by approximately 54 months from the start of the trial, providing >85% power to detect a 15% risk reduction with lorcaserin HCl, assuming an annual background rate of 3.5%, 15-month accrual period, 5% annual drop-out rate, $\alpha = 0.05$, and a 2-sided test (revised per Amendment 02)

Key Secondary Endpoint (revised per Amendment 02)

- For 457 events of conversion to T2DM in subjects who are prediabetic at the time of enrollment (~33%) to have occurred by approximately 54 months from the start of the study, providing 86% power to detect a 25% risk reduction with lorcaserin HCl, assuming an annual background rate of 4%, 15-month accrual period, 5% annual dropout rate, $\alpha = 0.05$ and a 2-sided test. (revised per Amendment 02)

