#### 4 DETERMINATION OF SAMPLE SIZE

A sample size of 12,000 subjects should provide the required power for the primary endpoints and key secondary endpoint as follows:

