### **Primary Endpoints (revised per Amendment 02)**

- For 460 MACE events to have occurred by approximately 43 months from start of the trial, providing 95% power to exclude a noninferiority margin of 1.4, assuming an annual background rate of 1.5%, 15-month accrual period, 5% annual drop-out rate,  $\alpha = 0.025$ , and a 1-sided test
- For 1401 MACE+ events to have occurred by approximately 54 months from the start of the trial, providing > 85% power to detect a 15% risk reduction with loreaserin HCl, assuming an annual background rate of 3.5%, 15-month accrual period, 5% annual dropout rate,  $\alpha = 0.05$ , and a 2-sided test

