#### **Key Secondary Endpoint (revised per Amendment 02)**

• For 457 events of conversion to T2DM in subjects who are prediabetic at the time of enrollment ( $\sim$ 33%) to have occurred by approximately 54 months from the start of the study, providing 86% power to detect a 25% risk reduction with lorcaserin HCl, assuming an annual background rate of 4%, 15-month accrual period, 5% annual dropout rate,  $\alpha = 0.05$  and a 2-sided test.

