- Proportions of subjects with prediabetes at Baseline who develop new diagnosis of diabetic retinopathy or new diagnosis of diabetic neuropathy by EOS (revised per Amendment 01)
- Proportions of subjects with T2DM at Baseline who develop new diagnosis of diabetic retinopathy or new diagnosis of diabetic neuropathy by EOS (revised per Amendment 01)

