- Proportion of subjects with reduction in the number of OAD medications or reduction in the dosage of OAD medications in the following subpopulations of subjects with T2DM at Baseline will be analyzed using logistic regression including treatment as factor. Comparison between lorcaserin HCl and placebo will be made at 6 months. The odds ratio, p-value and 2-sided 95% CI will be calculated. The T2DM Analysis Set will be used for this analysis, in the following subpopulations:
  - o Subjects with (HbA1c > 7%) at Baseline
  - o Subjects who are on monotherapy with oral antidiabetic agent at Baseline
  - Subjects with early T2DM (duration of diagnosis of diabetes is less than 5 years) at Baseline
- Proportions of subjects with at least a 1-stage reduction in an obesity-related complication (prediabetes, metabolic syndrome, T2DM, hypertension, and hypertriglyceridemia/dyslipidemia), incidence of other obesity-related complications will be collected through AE reports, medical history, and use of concomitant medications, will be analyzed using logistic regression including treatment as factor. Comparison between lorcaserin HCl and placebo will be made at 1 year and EOS. The odds ratio, p-value and 2-sided 95% CI will be calculated. The ITT Analysis Set will be used for this analysis.

Logistic regression including treatment as factor will be used for the following endpoints. Comparison between lorcaserin HCl and placebo will be made at EOS. The odds ratio, p-value and 2-sided 95% CI will be calculated.

The Prediabetes Analysis Set will be used for the following analyses: (revised per Amendment 01)

- Proportions of subjects with prediabetes at Baseline who develop new diagnosis of diabetic retinopathy at EOS.
- Proportions of subjects with prediabetes at Baseline who develop new diagnosis of diabetic neuropathy at EOS.

The T2DM Analysis Set will be used for the following analyses: (revised per Amendment 01)

- Proportions of subjects with T2DM at Baseline who develop new diagnosis of diabetic retinopathy at EOS.
- Proportions of subjects with T2DM at Baseline who develop new diagnosis of diabetic neuropathy at EOS.

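### The retinopathy and neuropathy comparisons ignore time at risk, the CV stratum and complications present at Baseline, so their odds ratios can be biased if retention or survival differs by arm

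*SAP*

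**What the plan says.** SAP 5.8 covers new retinopathy and new neuropathy, separately, in the Prediabetes and T2DM Analysis Sets: "Logistic regression including treatment as factor will be used for the following endpoints. Comparison between lorcaserin HCl and placebo will be made at EOS". An odds ratio, p-value and 95% CI are reported. Protocol 9.7.1.8 specifies the same model.

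The endpoint list in SAP 5.1.4 is worded cumulatively: "Proportions of subjects with T2DM at Baseline who develop new diagnosis of diabetic retinopathy or new diagnosis of diabetic neuropathy by EOS". Protocol 9.5.1.4 collects these diagnoses through AE monitoring, and Table 4 of the protocol schedules no eye or nerve examination. SAP 8.5 defines a subject's individual EOS as the last visit or contact. However, SAP 3.3 ties the EOS visit to Sponsor Notification of Study Completion, and SAP Table 8 lists EOS at Month 58.

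No section says how an undiagnosed subject who leaves or dies is scored for these endpoints. SAP 5.3.5 deals with MACE/MACE+ and vital status, the multiple imputation in SAP 5.4.1.1 is for MACE superiority and MACE+, and Table 7 gives censoring rules for the renal and glucose endpoints.

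SAP 5.4 assigns time-to-event endpoints, including exploratory ones, a Cox model with treatment and CV stratum. The stratum is left out for populations without T2DM.

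**The concern.** A yes/no outcome counted up to last contact depends on how long each subject was observed. If one arm is observed for less time, it has fewer chances to record a diagnosis, and its odds fall without any drug effect. A treatment-only logistic model cannot separate the two. The trial itself tests whether lorcaserin lowers all-cause mortality, so a difference in time at risk is possible in principle.

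Two smaller weaknesses go with this. The T2DM set spans both randomisation strata, but the model leaves the stratum out. The T2DM set also has no exclusion for retinopathy or neuropathy already present at Baseline, so some subjects in the denominator cannot have a new diagnosis.

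This is the only inferential comparison planned for the microvascular objective. The TEAE tables in SAP 5.6.2 would also show these terms by arm, but only descriptively.

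**Working it through.** **Inputs from the documents.** SAP section 4 gives, for T2DM conversion, "assuming an annual background rate of 4%, 15-month accrual period, 5% annual dropout rate", with 457 events by about 54 months, N = 12,000 of whom about 33% are prediabetic (3,960), and "providing 86% power to detect a 25% risk reduction with lorcaserin HCl". SAP Table 1 puts T2DM at 50% (about 6,000). Allocation is 1:1.

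**Assumptions of this check.** Uniform accrual and exponential event and drop-out times. The documents give no diagnosis rates and no arm-specific drop-out, so those figures are illustrative.

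**Step 1: reproduce the plan's figure.**
- Power = Φ(|ln 0.75| × √(457/4) − 1.96) = Φ(0.2877 × 10.69 − 1.96) = Φ(1.115) = 86.8%, against the stated 86%.
- Expected events, with hazards 0.04 and 0.03, drop-out hazard 0.05 and 3,960 subjects, are 456.5, against the stated 457.

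The plan's drop-out and accrual inputs therefore work as a model of follow-up.

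**Step 2: share leaving before a 54-month close.** Follow-up f runs from 54 − 15 = 39 months (3.25 years) to 54 months (4.5 years), mean 3.875 years.
- 5% as a hazard: 1 − (e^(−0.1625) − e^(−0.225)) / (0.05 × 1.25) = 1 − 0.0515/0.0625 = 17.6%.
- 5% as an annual probability: 1 − 0.95^3.25 = 15.4% for the last subject enrolled, 1 − 0.95^4.5 = 20.6% for the first, and 18.0% on average.

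These figures are drop-out only. The documents give no all-cause death rate.

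**Step 3: odds ratio with leavers scored as non-events.** For diagnosis rate λ and drop-out rate d, at mean follow-up,

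p = λ/(λ+d) × (1 − e^(−(λ+d) × 3.875)).

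At λ = 1% per year with no drug effect, for 6% (lorcaserin) against 4% (placebo):
- p at 6% = 0.1429 × (1 − e^(−0.27125)) = 0.0339
- p at 4% = 0.2000 × (1 − e^(−0.19375)) = 0.0352
- odds ratio = 0.0351/0.0365 = 0.962

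Averaging over entry dates, for diagnosis rates of 0.5% to 5% per year and a true odds ratio of 1:

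| Drop-out per year, lorcaserin / placebo | Odds ratio |
|---|---|
| 5% / 5% | 1.000 |
| 6% / 4% | 0.957 to 0.962 |
| 4% / 6% | 1.039 to 1.044 |
| 7% / 3% | 0.917 to 0.926 |

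With equal drop-out and a true hazard ratio of 0.8, the odds ratio is 0.787 to 0.799 against 0.784 to 0.798 without drop-out, a shift of at most 0.003.

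**Step 4: compare with precision.** At 1% per year and 5% drop-out, p = 0.0346. In the T2DM set this gives about 207 events, SE(log OR) = √(2/(3,000 × 0.0346 × 0.9654)) = 0.14, and a null 95% CI of about 0.76 to 1.32. In the prediabetes set it gives about 137 events and about 0.71 to 1.41. The 6%/4% shift, |ln 0.962| = 0.039, is about 0.27 of the T2DM standard error.

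**Step 5: baseline cases.** If the same share k of each arm already has the complication, each arm's proportion is multiplied by (1 − k) and their ratio does not change. This blurs what the proportion means but does not favour an arm.

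**The case against.** The strongest reply is that nothing in the documents shows a bias. Entry dates spread follow-up over 39 to 54 months, but 1:1 randomisation balances that spread, and the plan assumes one drop-out rate for both arms. The conduct rules also work against loss: subjects who stop drug stay in follow-up, patient-finder services are used, and complete withdrawal of consent is expected to be very rare (protocol 9.5.5). All of this stands. A reader might infer that the planned odds ratio is biased because follow-up is unequal, or that 18% leave or die. The documents support neither: bias needs retention or survival that differs by arm or is related to the outcome, and the 18% excludes deaths.

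The second reply is that the scoring rule is already implied. The cumulative endpoint wording, AE collection, the individual EOS date and the ITT-based analysis sets point to a diagnosis recorded by last contact, yes or no. That is the natural reading, and a completers analysis has little support. But the SAP does not state the rule for these endpoints, the Month 58 EOS entry pulls the other way, and the implied rule is the one that lets unequal time at risk into the odds ratio.

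The third reply is that a Cox model is not free of problems. AE onset dates are dates of detection, and SAP 13.3 can impute a partial or missing onset date to the first-dose date, which puts events near time zero. Censoring does not cure drop-out related to the outcome, and censoring at death gives a cause-specific hazard ratio. These limits are real. They are reasons to keep the logistic model beside the Cox model, not reasons to ignore follow-up time.

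**Conclusion.** The point holds as a minor one. The planned model leaves out time at risk, the CV stratum in the T2DM set and complications present at Baseline, and its scoring rule is implied rather than stated. About 18% of subjects (17.6% to 18.0%) would leave before a 54-month close on the plan's own rate. The effect on the odds ratio is essentially nil if the arms lose subjects equally, and about 4% for a difference of 6% against 4% per year. That shift is well inside the sampling error expected at a 1% per year diagnosis rate. These sizes rest on uniform accrual, exponential times, drop-out unrelated to the diagnosis, and diagnosis and arm-specific drop-out rates that are illustrative. The endpoints are exploratory and outside the testing hierarchy, so no primary or key secondary conclusion is at risk.

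**What to change.** In SAP 5.8, make the main analysis of each endpoint time from randomization to first AE-reported diagnosis, using the Cox model of SAP 5.4:

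- Censor event-free subjects at the earlier of last contact and death, in line with SAP 8.5 and Table 7.
- Include the CV stratum in the T2DM set. The prediabetes set needs none, because by design all subjects without T2DM have established CV disease.
- Exclude from each analysis subjects with that complication at Baseline, identified from the recorded medical and diabetes history.
- Keep the protocol's logistic model as a supportive analysis, stating that undiagnosed leavers and deaths count as non-events.
- Report retention and death by arm in both sets, and the number of events with an imputed onset date.

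The cost is some SAP text and four Cox models on data already collected. Because this departs from protocol 9.7.1.8, record it in SAP Section 7. The remaining drawbacks are that onset dates are detection dates and that some are imputed under SAP 13.3.

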#### 6 INTERIM ANALYSES

There will be one interim analysis; when 460 adjudicated MACE events have occurred, the primary analysis for MACE will be conducted. This will be the analysis to rule out a hazard ratio of 1.4. If the non-inferiority margin is met, the study will continue to accrue events until the required number of MACE+ and diabetes conversion events have occurred.

The interim analysis for MACE endpoint will be performed by an independent statistician and governed by an independent DMC and is anticipated to occur on or before (approximately) July 2017. The interim analysis will be conducted according to a DMC Charter to establish whether the MACE primary objective has been achieved.

To maintain the integrity and credibility of the trial, procedures will be implemented to ensure the DMC and independent statistician have sole access to evolving information from the clinical trial regarding comparative efficacy and safety data aggregated by treatment group. Full details of the DMC procedures including primary responsibilities of the DMC, its relationship with other trial components, its membership, and the purpose and timing of its meetings will be documented in the DMC Charter. These details will also include procedures to ensure confidentiality and proper communication, the safety and statistical monitoring guidelines to be implemented by the DMC, and an outline of the content of the closed reports and open reports that will be provided to the DMC. See Appendix 13.1.2 for the DMC charter. In addition, the Study Integrity Charter in Appendix 13.1.2, describes the membership, responsibilities, data access, and firewalls, when 460 adjudicated MACE events are achieved and the IA is conducted.

At the interim analysis for MACE, the estimate of the hazard ratio of lorcaserin HCl to placebo and the corresponding one-sided 97.5% CI will be calculated. Non-inferiority between lorcaserin HCl and placebo will be declared if the upper limit of the 97.5% CI is less than the non-inferiority margin of 1.4. Otherwise, lorcaserin HCl will be declared as not noninferior to placebo and the trial will stop.

If non-inferiority between lorcaserin HCl and placebo is confirmed when 460 adjudicated MACE events are observed at approximately 43 months from the start of the study, then the study will be continued to observe 1401 adjudicated MACE+ events at approximately 54 months from the start of the study, and 2.5 years median treatment duration.

#### 6.1 INTERIM ANALYSIS STATISTICAL ANALYSIS PLAN

At the interim analysis; when 460 adjudicated MACE events have occurred, the following analysis will be performed using a Cox proportional hazards model that includes factors for treatment and stratification variable (presence of established CV disease or CV risk factors without established CV disease).

Details of the censoring algorithm for the MACE endpoint is presented in Section 8.5.1.

#### 6.1.1 Primary Endpoint Analysis for time to MACE

Primary endpoint analysis for time to MACE for Non-inferiority: The estimate of the hazard ratio of lorcaserin HCl to placebo and the corresponding one-sided 97.5% CI will be calculated. Non-inferiority of lorcaserin HCl to placebo will be declared if the upper limit of the 97.5% CI is less than the non-inferiority margin of 1.4. The Total Time Analysis Population will be used.

#### 7 CHANGES IN THE PLANNED ANALYSES

The following exploratory endpoints were not analyzed.

- Proportion of subjects with reduction in the number of OAD medications or reduction in the dosage of OAD medications in the following subpopulations of subjects with T2DM at Baseline will be analyzed using logistic regression including treatment as factor. Comparison between lorcaserin HCl and placebo will be made at 6 months. The odds ratio, p-value and 2-sided 95% CI will be calculated. The T2DM Analysis Set will be used for this analysis, in the following subpopulations:
  - o Subjects with (HbA1c > 7%) at Baseline
  - o Subjects who are on monotherapy with oral antidiabetic agent at Baseline
  - Subjects with early T2DM (duration of diagnosis of diabetes is less than 5 years) at Baseline.

Reason: Difficulty in defining reduction or change in dosage OAD medications and interpretation of results.

• Proportions of subjects with at least a 1-stage reduction in an obesity-related complication (prediabetes, metabolic syndrome, T2DM, hypertension, and hypertriglyceridemia/dyslipidemia), incidence of other obesity-related complications will be collected through AE reports, medical history, and use of concomitant medications, will be analyzed using logistic regression including treatment as factor. Comparison between lorcaserin HCl and placebo will be made at 1 year and EOS. The odds ratio, p-value and 2-sided 95% CI will be calculated. The ITT Analysis Set will be used for this analysis.

Reason: It was determined that this population will show no change in Obesity Staging

#### 8 DEFINITIONS AND CONVENTIONS FOR DATA HANDLING

The baseline value for efficacy and safety will be defined as the most recent value reported prior to or at randomization. Adverse events with missing severity will be assigned the highest severity. Adverse events with missing relationship will be assigned as related, as part of a sensitivity analysis. Adverse events and Concomitant Medications with partial dates will be imputed according the algorithm defined in the SDTM specifications, also included in Appendix 13.6.

#### **DEFINITIONS**

• Clinically Notable Changes in Blood Pressure:

#### Systolic blood pressure

Increase from baseline of ≥ 20 mm Hg

Post-baseline value > 160mm Hg

Post-baseline value > 160mm and Increase ≥ 20 mm Hg

Decrease from Baseline of  $\geq 20 \text{ mm Hg}$ 

Post-baseline value < 60 mm Hg

Post-baseline value < 60mm and Decrease ≥ 20 mm Hg

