#### 5.6.4 Vital Signs

Descriptive statistics for vital signs parameters (i.e., diastolic and systolic BP, pulse, weight) and changes from Baseline will be presented by visit and treatment group. Descriptive statistics and changes from Baseline will also be presented by visit and treatment group for waist and hip circumference. In addition, systolic and diastolic blood pressure will be summarized by clinically notable changes (see Section 8).

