#### Diastolic blood pressure

Increase from baseline of  $\geq$  20mm Hg

Post-baseline value > 100mm Hg

Post-baseline value > 100mm Hg and Increase ≥ 20mm Hg

Decrease from Baseline of  $\geq 10 \text{ mm Hg}$ 

Post-baseline value < 50 mm Hg

Post-baseline value < 50 mm Hg and Decrease ≥ 10 mm Hg

• Treatment Compliance: Treatment compliance will be determined for the entire double blind phase. Subjects taking BID or QD dosing will be considered as been compliant. The total tablets taken = total tablets dispensed – total tablets returned.

Compliance = 100 x Total tablets taken / Total tablets Expect

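### The low systolic cut-off of 60 mm Hg leaves two of the three low-systolic rows in the blood pressure safety table empty or nearly empty

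*SAP*

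**What the plan says.** SAP 5.6.4 (Vital Signs) states that "systolic and diastolic blood pressure will be summarized by clinically notable changes", and points to SAP Section 8 for the definitions. This is in addition to descriptive statistics by visit and treatment group.

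Section 8 gives three rows for low systolic pressure:

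- a fall from Baseline of at least 20 mm Hg, with no absolute limit (the row beginning "Decrease from Baseline of");
- "Post-baseline value < 60 mm Hg";
- "Post-baseline value < 60mm and Decrease ≥ 20 mm Hg".

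The three low-diastolic rows have the same layout: a fall of at least 10, "Post-baseline value < 50 mm Hg", and "Post-baseline value < 50 mm Hg and Decrease ≥ 10 mm Hg". The absolute high limits are "Post-baseline value > 160mm Hg" for systolic and "Post-baseline value > 100mm Hg" for diastolic.

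The SAP revision history shows that these definitions were added in version 3.0 at the request of the clinical team. It gives no reason for the value 60. The protocol's own vital-signs analysis (Section 9.7.1.10) has no such categories.

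**The concern.** The low systolic limit does not fit the plan's other blood pressure figures. Two of the three low-systolic rows depend on it, and the second of these lies wholly inside the first, so if the first is empty both are. The remaining row has no lower limit, so a fall from 170 to 150 counts in it just as a fall from 105 to 85 does.

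Low pressure is worth tabulating properly in this trial. Protocol Section 7.1 reports that the drug improved blood pressure in earlier studies. Treated hypertension is one of the qualifying risk factors in Protocol 9.3.1, and antihypertensive drugs may be adjusted during the study (9.4.7.2). Two rows of zeros or near-zeros in both arms could be taken as reassurance, although the threshold had almost no capacity to pick out low systolic readings.

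**Working it through.** The plan states no figure on this point to reproduce. The check has four steps.

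**1. Distance between systolic and diastolic limits**

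| Pair | Source | Gap (mm Hg) |
|---|---|---|
| 160 / 100 | SAP Section 8, high limits | 160 − 100 = 60 |
| 140 / 90 | Protocol 9.3.1 (hypertension) and SAP Table 2 (subgroups) | 140 − 90 = 50 |
| 60 / 50 | SAP Section 8, low limits | 60 − 50 = 10 |

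**2. What the combined rows can separate**

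A combined row is meant to set apart subjects who moved from those already beyond the limit.

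- Systolic below 60 without a fall of 20 requires a Baseline below 60 + 20 = 80. Such subjects should be very rare, so the combined row nearly duplicates the plain one.
- Systolic above 160 without a rise of 20 requires only a Baseline above 160 − 20 = 140.
- Diastolic below 50 without a fall of 10 requires a Baseline below 50 + 10 = 60.

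**3. Expected readings below 60**

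Inputs from the documents: about 12,000 randomized (SAP 3.3), and 14 scheduled post-baseline vital-sign visits, counted from Protocol Table 4 (Months 3, 6, 12, 18, 24, 28, 32, 36, 40, 44, 48 and 52, EOT, EOS). The largest possible number of scheduled readings is 12,000 × 14 = 168,000. Not every subject reaches every visit, so the true number is smaller.

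Assumptions: systolic readings are normal with mean 125 to 135 and SD 13 to 20. Neither document gives a mean or SD.

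Expected readings = 168,000 × Φ((60 − mean)/SD). For mean 125 and SD 20: (60 − 125)/20 = −3.25, Φ = 0.000577, and 168,000 × 0.000577 ≈ 97.

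| Mean | SD 13 | SD 15 | SD 18 | SD 20 |
|---|---|---|---|---|
| 125 | 0.05 | 1.2 | 26 | 97 |
| 130 | 0.01 | 0.26 | 8.5 | 39 |
| 135 | 0.00 | 0.05 | 2.6 | 15 |

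The largest entry is 97/168,000 = 0.058% of readings. These are readings; the number of subjects cannot be larger.

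**4. The neighbouring rows under similar assumptions**

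- Diastolic below 50, with assumed mean 72 to 80 and SD 9 to 11: about 72 to 3,822 of 168,000 readings.
- Systolic fall of at least 20, with no true mean change, SD 15 to 18 and within-subject correlation ρ of 0.4 to 0.6 (all assumed). The SD of change is SD × √(2(1 − ρ)). The lowest case is 15 × √0.8 = 13.4, and Φ(−20/13.4) = 6.8%. The highest is 18 × √1.2 = 19.7, and Φ(−20/19.7) = 15.5%. That is about 816 to 1,863 of 12,000 subjects at a visit with no drug effect at all.

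So the diastolic row and the fall-only row would be populated, while the two rows built on 60 would not.

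**The case against.** The strongest reply is that the rest of the safety output covers the gap. SAP 5.6.4 also gives blood pressure and its change by visit and arm, and SAP Section 5 says descriptive statistics include the minimum, so the lowest systolic value in each arm at each visit is reported. The three low-diastolic rows do not depend on 60. The row for a fall of at least 20 mirrors the rise row and, in a randomized comparison, can show an imbalance between arms even though it is nonspecific. Hypotension reported as an adverse event would appear in the tables of SAP 5.6.2. All of this stands. A reader might infer from the near-empty rows that hypotension cannot show in the safety summary; the documents contradict that.

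These outputs still do not do the job of the two rows. A minimum is one value per arm and visit, not a count of subjects. The adverse event tables depend on an investigator reporting the reading. The diastolic rows measure something else. The fall-only row mixes low pressure with ordinary variation and misses a subject who starts low and falls by less than 20.

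A second reply is that nothing in the SAP requires the systolic and diastolic limits to keep a fixed distance, and no row uses both. This also stands. The gap of 10 suggests an entry error, but the value appears twice and the documents do not prove a mistake.

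Third, without a blood pressure distribution in the documents, it cannot be said that the rows will certainly be empty. That is right: isolated very low readings are possible, and empty or nearly empty is as far as the evidence goes.

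**Conclusion.** The point holds as a minor one. Two of the three low-systolic rows carry almost no information, so the notable-change table lacks a useful absolute threshold for low systolic pressure. The gaps and the nesting of the rows follow directly from the SAP. The size, about 0 to 97 of at most 168,000 scheduled readings, rests on the assumed normal distribution and is most sensitive to the SD: with SD 13 to 15 it is about one reading or none. The conclusion is the same across the range.

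Two stronger readings are not supported: that the safety summary as a whole is blind to hypotension, and that 60 is a proven typing error. The table is descriptive, with no test attached, and the analyses of MACE, MACE+ and conversion to T2DM are untouched.

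**What to change.** Before final unblinding, replace 60 mm Hg in both systolic rows of SAP Section 8 with a reporting threshold on the same footing as diastolic 50, and state the reason for the value. A limit of 90 is an example only: it is not sourced in either document, and the sponsor should choose and justify the figure. Under the assumptions above, a limit of 90 would catch about 45 to 6,730 of 168,000 readings, so the row would be populated. If 60 was intended, the SAP should say why.

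The cost is one number in the SAP, used in two rows, and the matching line in the table program. It changes a reporting threshold and no patient care. The timing matters, because a cut-off changed after unblinding could look data-driven.
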